In both sub-acute and chronic porcine ischemia-reperfusion injury (IR) models, MEMRI demonstrated a consistent anteroseptal infarct pattern from the mid-LAD IR injury). MEMRI of the hAMSC group revealed discrete foci of high contrast-to-noise ratio (CNR) *within* infarct and peri-infarct zones, which were absent in control group. These hyperintense foci increased in CNR over the 3-week and 6-week time course after cell delivery in comparison to the control group. To confirm the specificity of the positive MEMRI signal for hAMSC engraftment, the hAMSCs for one sub-acute and one chronic IR swine were modified with injection of ~20% herpes simplex virus-thymidine kinase (HSV-tk) PET reporter gene (PET-RG) transduced hAMSCs. Serial cardiac PET-CT scans (day 0, day 7, and day 21 or 38 after injection) were then performed using a specific 9-[ $\text{F}$ ]fluoro-3-(hydroxymethyl) butyl] guanine (F-FHBG) radioisotope, which are phosphorylated and retained only by the viable cells expressing PET-RG. At each time point, apical PET signal co-localized with the site of cell injection and MEMRI signal. Quantitative assessment of PET activity from these regions indicated significantly higher radiotracer uptake compared to surrounding myocardium by approximately 25-fold. When plotted according to the AHA 16-segment model, the integrated MEMRI and PET signal within each segment showed a significant linear correlation in both the sub-acute and chronic IR models. The increased MEMRI CNR tracked the survival of hAMSCs longitudinally, suggesting that the hAMSCs engrafted *in vivo* up to 6 weeks.

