#### Parameters to be Measured:

A standard physical assessment will be performed on the day of imaging (approximately 1-hour post dosing). Body temperature and respiration rate will be measured within 24 hours prior to dosing and at approximately 1- and 2-hours post dose. A standard 12-lead EKG will be performed both before and after the MR study to assure no significant EKG changes have occurred. Patient's hemodynamics will also be serially monitored. A baseline BP and HR will be performed before beginning the study. After EVP1001-1 contrast infusion, BP and HR will be measured every 2 minutes until 10 minutes post EVP1001-1 contrast infusion after which point a BP and HR will be measured every 5 minutes until the conclusion of the MEMRI and every 10 minutes until the conclusion of DEMRI study. There will be a 5-minute post administration observation interval outside the scanner. The patient will also have continuous EKG monitoring during this time. After the study, the patient will have another standard 12-lead EKG performed to compare with the pre-MRI 12-lead EKG. The patient's symptoms will be

CONFIDENTIAL

This material is the property of Stanford University. Do not disclose or use except as authorized in writing by the study sponsor

reassessed 1 hour after infusion of the EVP1001-1 contrast. A differential and serum chemistry profile (with liver function test) will be performed within a month prior to administration of EVP1001-1 and within 24 hours post EVP1001-1. Adverse events (AEs) and discomforts will be recorded until discharge from the imaging center. At the 24 hour follow-up, the subject will be evaluated by telephone to determine if any AEs occurred from the time the subject left the imaging center. The subjects will have a contact number to report any AEs or to ask questions. Any clinically relevant changes from baseline in vital signs, ECG rhythm, clinical chemistries or physical condition and all AEs will be followed until resolution or until the outcome is known. Injection-associated discomforts will be recorded during administration and until imaging is completed. Primary efficacy will be based on determining whether the heart is normal or abnormal and if abnormal whether there is an infarction, ischemia or both. This provides the basis for calculating sensitivity, specificity, accuracy and predictive values. In addition, the location, size, conspicuity and associated confidence for any disease will be recorded.

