### **3.2 Primary Study Endpoints**

The key endpoints of this study include the assessment of safety, tolerance and efficacy of EVP1001-1. Safety and tolerance will be evaluated based on the nature and extent of AEs and injection-associated discomforts and changes in laboratory parameters, vital signs and ECG after administration of EVP1001-1. Effects, if any, of EVP1001-1 on QT/QTc intervals will be determined by comparing the intervals before and after EVP1001-1 across the full HR range for each patient, including use of individual correction of QT by RR. All subjects who receive EVP1001-1 will be included in the analyses. Pre- and post-dose results will be compared for vital signs, clinical laboratory parameters, ECG parameters and hemodynamic parameters to identify individual changes from baseline and potential systematic shifts. The presence or absence of infarcts and/or ischemic areas relative to the current clinical standard (by echo and gadolinium-based cardiac MRI) along with comparison to patient outcomes will determine efficacy.

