### **3.3 Secondary Study Endpoints**

In addition, location, size, conspicuity, confidence, wall motion deficits and related diagnostic information will be assessed.

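### No rule requires a MEMRI defect to match the reference site, so a misplaced defect can count as a true positive in primary efficacy

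*Combined protocol and SAP*

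**What the plan says.** Section 3.1, under Parameters to be Measured, defines the read-out: "Primary efficacy will be based on determining whether the heart is normal or abnormal and if abnormal whether there is an infarction, ischemia or both". It continues: "This provides the basis for calculating sensitivity, specificity, accuracy and predictive values". Location then appears as an addition: "In addition, the location, size, conspicuity and associated confidence for any disease will be recorded".

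Section 3.2 defines efficacy as "The presence or absence of infarcts and/or ischemic areas relative to the current clinical standard" ("by echo and gadolinium-based cardiac MRI"), and adds a comparison with patient outcomes. Section 3.3 places location among the secondary endpoints: "In addition, location, size, conspicuity, confidence, wall motion deficits and related diagnostic information will be assessed".

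Three other places bear on the point:

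- Section 2 makes Aim 1 the description of injury around the infarct, in both ventricles and atria. Section 7.3 states the goal as better sensitivity and specificity for viable myocardium and the peri-infarct region (PIR).
- Section 3.1, General Design, says the two contrast image sets will be compared to identify viable, peri-infarct and infarct tissue. It gives no registration or matching rule and no link to the accuracy measures.
- Section 7.2 offers a t-test of MEMRI against DEMRI measurements and a Pearson correlation. Neither uses site.

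**The concern.** The accuracy measures rest on one call per heart. If the reference shows an infarct and MEMRI shows an infarct, the pair agrees, and no stated rule asks whether both are in the same wall, or even the same chamber. A lateral MEMRI defect paired with a septal DEMRI scar could therefore be a true positive.

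Aim 1 and the goal in section 7.3 are about where tissue is viable, injured or dead. A whole-heart score cannot separate correct tissue mapping from a defect anywhere, so it may overstate performance on the property that the trial is meant to test.

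**Working it through.** **1. What the text provides.** The sections on endpoints, design and statistics were compared for any rule on site.

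| Place | What is compared | Does site have to match? |
|---|---|---|
| 3.1, Parameters to be Measured | Whole-heart call | No; location recorded in addition |
| 3.2 | Presence or absence against echo and gadolinium MRI; patient outcomes | No |
| 3.1, General Design | Tissue class on two image sets | Not stated; not tied to accuracy |
| 3.3 | Location, size and other features | Secondary; no agreement measure given |
| 7.2 | Measurements (t-test, correlation) | No |

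**2. Plan's own figure.** There is none to reproduce. The documents give no assumed sensitivity, specificity or sample size for the presence/absence endpoint. The calculation in section 7.1 concerns a mean difference in a continuous signal and bears on this point neither way.

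**3. How unmatched scoring raises sensitivity.** All inputs are assumptions: 16 segments, 4 of them diseased, correctly located sensitivity *s*, and an independent false-defect rate *f* in each of the 12 healthy segments. A patient counts as positive if the true lesion is found or if any false defect appears elsewhere:

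patient-level sensitivity = s + (1 − s) × [1 − (1 − f)^12]

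For s = 70% and f = 2%: 1 − 0.98^12 = 0.215, and 0.70 + 0.30 × 0.215 = 0.765.

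| Correctly located sensitivity | f = 2% | f = 5% | f = 10% |
|---|---|---|---|
| 50% | 60.8% | 73.0% | 85.9% |
| 70% | 76.5% | 83.8% | 91.5% |
| 90% | 92.2% | 94.6% | 97.2% |

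The excess runs from about 2 points (92.2 − 90) to about 36 points (85.9 − 50). If the same *f* applied to disease-free hearts, patient-level specificity would be (1 − f)^16 = 72.4%, 44.0% and 18.5%. The larger excesses would therefore show up as poor specificity. A true lesion drawn in the wrong place would not.

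**4. No-information limit.** The pilot extents in sections 1.1 and 1.4 are DEMRI 39% and MEMRI 16%. On 16 segments these are 0.39 × 16 = 6.2 and 0.16 × 16 = 2.6, taken as 6 and 3. If the MEMRI defect were placed at random:

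- no shared segment: C(10,3)/C(16,3) = 120/560 = 21%;
- mean share of the MEMRI defect inside the scar: 6/16 = 37.5%.

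With 3 segments on each scan, which sets the pilot DEMRI extent aside, no overlap occurs in C(13,3)/C(16,3) = 286/560 = 51%. Every such patient would still be a whole-heart true positive.

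**5. Site also matters for the PIR.** Sections 1.1 and 7.1 read the DEMRI-minus-MEMRI volume difference as PIR. On the pilot means this is 39 − 16 = 23 points. If *o* is the overlap of the two regions, the DEMRI-positive, MEMRI-viable share is 39 − o. It equals 23 only when the whole MEMRI defect lies inside the DEMRI scar (o = 16), and it is 39 when they do not overlap (o = 0).

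**6. Why plain segment scoring will not do.** With 6 DEMRI and 3 MEMRI segments, a perfectly placed MEMRI defect scores 3/6 = 50% segment sensitivity, because the hypothesized PIR is counted as missed.

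**The case against.** The strongest reply is that silence is not a rule. The protocol never says that defects in opposite walls agree, section 3.2 does not state a unit of analysis, and readers might apply a site match in practice. This stands as far as it goes: that a misplaced defect is credited is an inference from a missing rule. But section 3.1 makes the heart the object of the call and derives the accuracy measures from it, so the plan as written permits that result.

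Three stronger readings are tempting, and the documents do not support them:

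- A reader might infer that efficacy is presence or absence and nothing else. Section 3.2 adds patient outcomes, and section 3.1 separates infarction from ischemia, so a wrong type could be scored as wrong. Neither checks site.
- A reader might take the 21% and 51% as this trial's likely error. They need random placement, and the protocol's data point the other way. Sections 1.1 and 1.4 report negligible uptake in the infarct core, reduced uptake in the PIR and higher uptake in normal tissue. In section 1.3 both scans correlated with stained infarct volume, and most of the discrepancy lay in the PIR.
- A reader might infer from section 1.3 that the sponsor dropped its own segmental method. The data "plotted according to the AHA 16-segment model" there were MEMRI and PET signals for stem-cell engraftment. The animal comparison of MEMRI with DEMRI used infarct volumes.

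It is also fair to say that location is already planned as a secondary endpoint, so part of this is a question of hierarchy. Even there, no agreement measure for location is given.

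**Conclusion.** The point holds as a gap in the primary efficacy definition: accuracy is calculated from a whole-heart call, location is secondary, and no location-match rule exists. A misplaced MEMRI defect can therefore be a true positive in a trial whose first aim is regional.

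This conclusion rests on the text and needs no numerical assumption. Its size is not known. The excess of about 2 to 36 points depends on assumed segment counts, independence and false-defect rates. The random-placement figures are a no-information limit and not a forecast. The documents do not show that MEMRI defects are in fact misplaced; they show that the primary measures could not reveal it if they were.

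**What to change.** In sections 3.1 and 3.2, before images are read:

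- Count a patient-level true positive only when the MEMRI defect lies in the same prespecified region as the reference defect. Use AHA segments or coronary territories for the ventricle and a simple stated region map for the atria. State the minimum overlap and which reference reading fixes the site.
- State that a diseased heart with only a mismatched defect is a miss for sensitivity and is not a true positive in the positive predictive value.
- Keep the unmatched whole-heart call as a descriptive summary.

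In section 7.2, add a segment-level analysis with intervals clustered by patient (GEE or a patient bootstrap). Report the share of the MEMRI defect that lies inside the DEMRI region. Class DEMRI-positive, MEMRI-viable segments as PIR and not as MEMRI false negatives. This class adopts the protocol's account of the PIR and does not test it. The segments that count against that account are MEMRI defects outside the DEMRI region, and they should be reported.

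Cost: location and size are already recorded, so for the ventricle this is mostly wording and analysis. The documents contain no atrial map, and section 7.1 stresses how hard the thin atrial walls are to image, so most of the added reading time falls there. Reported agreement will probably be lower.

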## 1.1 Background

- This is a first-in-human clinical translation of manganese-enhanced MRI(MEMRI) to assess the peri-infarct injury in patients with patients with ischemic or dilated cardiomyopathy with an EF less than or equal to 50 or patients with paroxysmal or persistent atrial fibrillation
- and those who received stem cell therapy for these indications. The PI recently obtained an approval for an Investigational New Drug (IND # [REDACTED]) to conduct a clinical trial of MEMRI contrast agent (EVP1001-1, Eagle Vision, Downingtown, PA). Funding of this proposal will enable a clinical trial of 120 patients with ischemic or dilated cardiomyopathy with an EF less than or equal to 50 or patients with paroxysmal or persistent atrial fibrillation to evaluate the safety and efficacy of sequential acquisition of MEMRI and delayed-enhanced MRI (DEMRI) for precise tissue characterization of the peri-infarct region (PIR). This novel technique designed to integrate the biology of the viable cardiomyocytes with the anatomy of the scar will predict future cardiovascular events (CVE), in this highly morbid patient population. ICM and NICM are the primary etiology of advanced heart failure (HF) while ACM is a frequent sequela of HF. Today, HF is the leading diagnosis of hospital admission in the US. Our studies have confirmed a direct association between the presence of PIR and the occurrence of atrial and ventricular arrhythmia and remodeling, resulting in high morbidity and mortality in advanced HF. PIR has been recognized as an important substrate to trigger atrial and ventricular arrhythmias and stem cells may provide an alternative therapy for PIR. Studies employing DEMRI has identified atrial scar as the potential cause of atrial arrhythmia. This proposal contains novel hypotheses well-grounded on the following 2 innovations: (1) MEMRI for management of HF. An alternative approach is to employ manganese (Mn2+), which targets the viable myocardium. Mn2+ is specific to the L-type calcium channels and complements the non-viable scar delineated by DEMRI. The dual MEMRI-DEMRI approach will, therefore, identify the viable and, potentially, salvageable cardiomyocytes outside the core infarct zone but inside the PIR. Our recently published study demonstrated that an overlap of DEMRI and MEMRI signal denoted a significant number of live cardiomyocytes (MEMRI-positive) within the non-viable (DEMRI-positive) region. This innovation will profoundly impact the clinical management of the advanced HF patients and AA patients including atrial fibrillation. EVP1001-1 allows highly effective intracellular targeting of viable cardiomyocytes with high level of safety and unique magnetic properties. (2) Assessment of therapeutic response using MEMRI. EVP1001-1 is rapidly transported, intra-cellularly, to mitochondria rich tissue such as heart, liver, and kidney, demonstrating significant enhancement indicative of cell metabolism and viability. High dose clinical safety studies of SeeMoreTM with safety index of 45-90 correspond more favorably than the widely used clinical imaging agents (10-20 for iodinated X-ray products and 20-60 for gadolinium). This specific, non-perfusion dependent distribution due to active intracellular uptake is one of the key attributes that offers real-time assessment of therapeutic response, using cardiac cellular imaging. A clinical safety trial in 6 patients have demonstrated negligible uptake in the intra-infarct region (IIR), reduced uptake in the PIR, and significantly higher uptake in the normal tissue to generate positive signal. In this trial, the mean LVEF was 32±4%. The DEMRI vs. MEMRI (scar/myocardial volume) demonstrated significantly higher measurement of the scar by DEMRI in all patients (39±11%\* vs. 16±3%, \*p<0.01) These data indicate 2 important findings: 1) significant over-estimation of the scar by DEMRI and 2) quantitative difference of the scar volume between MEMRI and DEMRI delineates the PIR. This precise characterization allows accurate assessment of the efficacy of novel therapeutic agents in restoring the PIR at both cellular and tissue levels. EVP1001-1 is a new manganese (Mn)-based intravenous imaging agent being developed to enhance magnetic resonance imaging (MRI). While Mn has long been known to have desirable magnetic and kinetic properties for MRI, use in humans was not initially possible due to cardiovascular depression and electrocardiogram (ECG) changes, including prolongation of PR and QTc intervals, associated with intravenous administration. Chelation of Mn, as had been done with gadolinium for use with MRI, provided relevant safety, but sacrificed desirable magnetic and kinetic properties. EVP1001-1 provides Mn in a form that maintains the desired magnetic and kinetic properties while overcoming the cardiovascular toxicity of Mn. EVP1001 is taken up into heart cells (primarily via addition of calcium to avoid cardiotoxic effects; please refer to patent listed below). The potential to distinguish healthy heart tissue from unhealthy heart tissue based on a specific sustained pattern of enhancement provides a basis for evaluating the performance of EVP1001-1 in heart patients. MRI offers benefits over other imaging technologies. Relative to radioactive nuclear imaging procedures, MRI is 3- dimensional, provides good soft tissue discrimination, and is of high spatial and temporal resolution. These features have been reported to identify smaller defects (e.g., subendocardial infarcts) and match angiographic results more closely than other modalities such as SPECT. It may be possible to enhance the utility of MRI for heart disease further through the use of an imaging agent that is specifically taken up into heart cells. EVP1001-1 is the only cardiac-specific agent being developed for this purpose. Unlike nuclear perfusion agents, EVP1001-1 is not radioactive and does not require special handling, shielding, transport or storage. In addition, the specific pattern of enhancement achieved in the heart muscle persists

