#### *Primary Objective*

Specific Aim 1 evaluates the efficacy of MEMRI-DEMRI to characterize the peri-infarct injury in the ventricles and atria.

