## **3 Study Design**

### **3.1 General Design**

Prior to entry into this study, all subjects will sign an Informed Consent and will then undergo a physical assessment including medical history, details regarding their cardiac history, prescription and over-the-counter drug review,, vital signs, electrocardiogram (ECG), evaluation of the major organ systems, hematology, serum chemistries. In addition, female subjects will undergo a serum pregnancy test.

Starting 30 minutes before the cardiac MRI scan (CMR), the subjects will take 16 mgs of ondansetron by mouth. CMR imaging will subsequently take place and then EVP1001-1 will then be administered approximately 15 minutes into the scan for contrast enhanced images. EVP1001-1 will be administered intravenously over approximately one minute. The subjects will each receive 0.28 mL/kg of EVP 1001-1. All subjects will be monitored closely from before ondansetron administration until their discharge from the imaging center. Following MEMRI, delayed-enhanced MRI(DEMRI)is performed using 0.2mmol/kg gadolinium. We will compare the two different contrast enhanced images (EVP1001-1 vs Gadolinium) in determining the viable, peri-infarct, and intra-infarct myocardial tissue.

To ensure a high-quality image, if the participant heart rate is greater than 65 bpm and regular rhythm, metoprolol will be given. If the HR is 65 and irregular, metoprolol will be given if there

are no contraindications (see table 1 below)

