## 7 Statistical Plan

### 7.1 Sample Size Determination

The total number of 0 patients will power this study adequately, however as we have extended the protocol to include the atrial fibrillation participants (and extra 60 pts) the difficulty in imaging the atria, coupled with the thin atrial walls, means that we expect a difference in DEMRI volume of 40 (+ or - 20) in participants with early disease and 60 (+ or - 20) in participants with advanced disease. Accordingly, 60 participants will be needed for the additional cohort. Our published pre-clinical study in 13 swine demonstrated the infarct volume percentage difference of 9% between MEMRI and DEMRI ( $p<0.001$ ). This difference will enable significant delineation of the changes in the peri-infarct viability between the cell therapy and control arms. The preliminary porcine data presented above demonstrated a mean of 100% increase in the CNR of the peri-infarct region and a mean of 50% decrease in the scar volume, suggesting robust MEMRI signal detection of stem cell engraftment and increased peri-infarct viability. Furthermore, the clinical trial in 6 ICM patients demonstrated significant difference in the infarct volume between MEMRI defect and DEMRI enhancement. This difference between MEMRI and DEMRI represents PIR assuring reliable detection of the PIR. Employing these data, in order to detect a mean difference of 20% in MEMRI signal of stem cell engraftment and MEMRI-DEMRI signal of peri-infarct viability with a standard deviation of 5%, the t-test sample size calculation in this study has 90% power at the alpha 0.05 significance level, assuming an equal variance between the two distributions.

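### The primary efficacy call has no peri-infarct category, and if one gadolinium MRI read is both comparator and reference (alone or in a simple composite with echo), MEMRI cannot beat it on both sensitivity and specificity

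*Combined protocol and SAP*

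**What the plan says.** Section 2 sets the primary objective: "Specific Aim 1 evaluates the efficacy of MEMRI-DEMRI to characterize the peri-infarct injury in the ventricles and atria".

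The primary efficacy reading is described under Parameters to be Measured in Section 3.1: "Primary efficacy will be based on determining whether the heart is normal or abnormal and if abnormal whether there is an infarction, ischemia or both". It continues: "This provides the basis for calculating sensitivity, specificity, accuracy and predictive values". Section 3.2 gives the reference for infarcts and ischemic areas: "relative to the current clinical standard (by echo and gadolinium-based cardiac MRI) along with comparison to patient outcomes will determine efficacy". It does not say how echo, gadolinium MRI and outcomes are to be combined, and it names no unit of analysis.

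Elsewhere the protocol treats the peri-infarct region (PIR) as a volume difference. Section 1.1 says the "quantitative difference of the scar volume between MEMRI and DEMRI delineates the PIR". Section 7.1 says: "This difference between MEMRI and DEMRI represents PIR assuring reliable detection of the PIR". Section 3.1 plans the image comparison: "We will compare the two different contrast enhanced images (EVP1001-1 vs Gadolinium) in determining the viable, peri-infarct, and intra-infarct myocardial tissue". The Study Summary and Section 7.2 plan a t-test of MEMRI against DEMRI measurements, and Section 3.3 lists size among the secondary endpoints. None of these is designated primary.

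Sections 1.1 and 1.4 expect higher accuracy than gadolinium MRI, among other modalities, and say this study will evaluate it. Section 7.3 states a goal of improved sensitivity and specificity for viable myocardium and PIR, without naming a comparator.

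**The concern.** There are two problems, and both affect what the headline result can mean.

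First, a reading whose categories are normal, infarction, ischemia or both cannot report on peri-infarct injury. MEMRI and DEMRI could agree on every heart and the primary result would still be silent on the primary objective.

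Second, the reference includes the comparator. DEMRI is the only gadolinium scan described (Section 3.1), and Section 1.4 calls it the current gold standard. Section 1.3 nevertheless says that DEMRI overestimates non-viable scar. A test cannot lose to a competitor on a measure where the reference makes it perfect by definition. If the reference rule is left open until the data are in, it may also be chosen with the result in view.

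**Working it through.** **1. Objective against endpoint.** The objective is peri-infarct injury (Section 2). The primary call is normal or abnormal and, if abnormal, infarction, ischemia or both (Section 3.1). The endpoint text covers infarcts and ischemic areas (Section 3.2). Neither of the last two has a peri-infarct category.

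The six-patient pilot in ischemic cardiomyopathy (Sections 1.1 and 1.4) shows the consequence. Scar was 39±11% by DEMRI and 16±3% by MEMRI, a mean difference of 39 − 16 = 23 points. Taking ± as SD, the smallest value possible among n = 6 is mean − SD×(n−1)/√n = 16 − 3×5/2.449 = 9.9%. Every MEMRI defect was therefore at least 9.9%. If any defect is read as infarct, all six hearts agree and the 23 points do not appear in a heart-level call. This need not carry over to dilated cardiomyopathy or atrial fibrillation.

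**2. Reference, by logic.** Assume one DEMRI read is both comparator and part of the reference.
- DEMRI alone: DEMRI scores 100% on both measures, so MEMRI can at best tie.
- Positive if DEMRI or echo is positive: every reference-negative patient is DEMRI-negative, so DEMRI specificity is 100%.
- Positive only if both are positive: every reference-positive patient is DEMRI-positive, so DEMRI sensitivity is 100%.

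**3. Reference, by enumeration.** Cross-classify patients by MEMRI, DEMRI and echo (8 cells), with 0 to 3 patients per cell: 4^8 = 65,536 tables. Keep those with at least one reference-positive and one reference-negative patient. The entries count tables in which MEMRI exceeds DEMRI. They are counts of possibilities, not probabilities.

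| Reference | Tables | Sensitivity | Specificity | Both | Overall accuracy |
|---|---|---|---|---|---|
| DEMRI alone | 65,025 | 0 | 0 | 0 | 0 |
| Either positive | 61,425 | 9,600 | 0 | 0 | 3,200 |
| Both positive | 61,425 | 0 | 9,600 | 0 | 3,200 |
| Echo alone | 65,025 | 24,480 | 24,480 | 9,216 | not needed here |

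The echo-alone row shows that it is DEMRI in the reference that blocks improvement on both measures. Under the either-positive rule, MEMRI gains on DEMRI only in patients who are DEMRI-negative, echo-positive and MEMRI-positive. Under the both-positive rule it gains only in those who are DEMRI-positive, echo-negative and MEMRI-negative. Every other MEMRI–DEMRI disagreement counts against MEMRI. Any gain therefore comes from patients in whom echo contradicts DEMRI.

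**4. Adding outcomes.** A separate enumeration of 5 patients over 16 cells (MEMRI, DEMRI, echo, outcome) gives improvement on both measures in 0 of 6,930 tables under an any-positive rule and 0 of 6,930 under an all-positive rule. It is possible in 280 of 13,920 under two-of-three, 641 of 13,250 under (DEMRI or echo) and outcome, and 1,416 of 13,920 with outcome alone. The plan states none of these rules.

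**5. Precision of a paired volume difference.** Take n = 50 (Study Summary, Section 2) and assume every patient gives a usable pair. SD of the difference = √(a² + b² − 2rab); 95% CI half-width = 2.0096×SD/√50; limits of agreement = ±1.96×SD. The correlation r is not given, so its full range is shown.

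| Assumption | SD of difference (r = 1 / 0 / −1) | Half-width, points | Limits of agreement |
|---|---|---|---|
| Pilot SDs, a = 11, b = 3 | 8.0 / 11.4 / 14.0 | 2.3 / 3.2 / 4.0 | ±16 / ±22 / ±27 |
| Section 7.1 ±20 as DEMRI SD, MEMRI SD 3 | 17.0 / 20.2 / 23.0 | 4.8 / 5.7 / 6.5 | ±33 / ±40 / ±45 |
| Section 7.1 SD of 5% as SD of the paired difference | 5.0 | 1.4 | ±9.8 |

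The second row rests on the atrial statement in Section 7.1 that "we expect a difference in DEMRI volume of 40 (+ or - 20) in participants with early disease", read as an SD in the same units. Reading the pilot ± as a standard error does not fit the pilot's own p<0.01. A paired t-test would then give at best t = 23/(11 − 3) = 2.875 on 5 df, p = 0.035, and an unpaired one t = 23/√(11² + 3²) = 2.017 on 10 df, p = 0.071.

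**The case against.** **The peri-infarct comparison is already in the plan.** This is true. Sections 3.1, 7.1 and 7.2 and the Study Summary all contain a MEMRI–DEMRI comparison. A reader might infer that the plan omits peri-infarct tissue; the documents do not support that. The defect is one of designation: the comparison is not the primary endpoint, and the call that is primary cannot express it.

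**MEMRI could still be shown more accurate.** This stands in part. A reader might infer that MEMRI can never do better than DEMRI. That holds only with DEMRI as sole reference. Under either composite MEMRI can exceed DEMRI on one measure and on overall accuracy, and overall accuracy is closer to what Sections 1.1 and 1.4 claim. The fair criticism there is bias toward DEMRI.

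**Outcomes are part of the reference.** A reader might infer that no outcome is given at all. In fact Section 2 names cardiovascular events as Aim 2, and the Study Summary and Section 7.2 plan a Pearson correlation with clinical outcome. Outcomes could supply a reference without DEMRI. The visible text, however, gives no combination rule, no horizon and no accuracy analysis using them; the 30 days in Section 8.1 concerns adverse-event reporting. The flowchart listed in Section 14 is not visible, so this is limited to the text available.

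**Targets and reads may differ.** Section 7.3 speaks of viable myocardium and PIR and names no comparator, so the conflict on both measures arises only if DEMRI is meant. A separate clinical gadolinium scan or an independent read would loosen the identity, but none is described. If the test under study is the combined MEMRI-DEMRI read of Aim 1, DEMRI sits in both the test and its reference, which raises the same difficulty.

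**Conclusion.** The point holds in two parts. The primary efficacy call does not measure the primary objective, and this rests on the text alone. The second part is conditional: if one DEMRI read is both comparator and reference, MEMRI cannot be shown to improve on DEMRI in both sensitivity and specificity with DEMRI alone (0 of 65,025 tables) or with either simple composite with echo (0 of 61,425 each). That is the Section 7.3 goal if DEMRI is its comparator. Superiority on one measure or on overall accuracy remains possible under the composites (overall accuracy in 3,200 of 61,425 tables each), but only through echo–DEMRI conflicts. Other combination rules, including some with outcomes, are not ruled out; the plan simply states none.

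The precision figures describe the proposed replacement, not the defect. They assume 50 usable pairs. Other sections give 60 or 120 patients, and some patients with atrial fibrillation or dilated cardiomyopathy may have no infarct to measure.

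**What to change.** (a) In Sections 3.1 and 3.2, treat DEMRI as the comparator. Report MEMRI against DEMRI as positive and negative percent agreement with 95% CI, not as sensitivity and specificity. Report any comparison with echo separately.

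(b) In Sections 3.2 and 7.2, name the within-patient MEMRI–DEMRI scar volume difference as the efficacy measure for PIR. Analyse it as paired, with 95% CI and limits of agreement, separately for ventricles and atria. State that it quantifies the difference and neither validates the PIR nor shows which method is right. If fewer than 50 patients contribute a pair for a chamber, the intervals will be wider than those above.

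(c) In Section 7.3, do not claim improved sensitivity and specificity over DEMRI on a reference that contains DEMRI. In Sections 1.1 and 1.4, do not say on such a reference that higher accuracy than gadolinium MRI will be evaluated. Keep these claims only if a pre-specified reference without DEMRI, such as a defined clinical outcome with a stated event and horizon, is applied to both methods in the same patients.

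The cost of (a) to (c) is low: endpoint, analysis and background wording, using images already planned. Keeping an accuracy claim through outcomes costs more, because event, horizon and follow-up must be defined. The price is a headline of agreement and difference in place of diagnostic superiority.
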